8.2. Recording of Adverse Events

At each contact with the subject, the investigator or study staff will seek information about adverse events by specific questioning and, if appropriate, by examination. Information on all AEs will be recorded immediately in the source document, and also in the appropriate AE section of the case report form (CRF). AEs will be tracked using the HSC IRB AE tracking form or data management tool (See Section 9.3) to be reviewed by Site Investigator on a monthly and ad hoc basis, depending on severity and expected/unexpected nature of the event. All subjects will have study compliance calls every two weeks during which AEs can also be reported.

All AEs occurring during the study period will be recorded. The clinical course of each event will be followed until resolution, stabilization, or until it has been determined that the study treatment or participation is not the cause. SAEs that are still ongoing at the end of the study period will be followed up to determine the final outcome. Any SAE that occurs after the study period and is considered to be possibly related to the study treatment or study participation will be recorded and reported per Institutional policy and according to FDA requirements.

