3.2. General Design

This is a single center, open-label, randomized controlled trial. 20 completed subjects are planned. Each subject will be randomized to either the experimental group of dapagliflozin 10mg daily for 12 weeks or the control group of nutritional counseling for weight loss. Healthspan and clinical evaluations will be taken at baseline and at weeks 10-12 of the study.

Screening data will be reviewed to determine subject eligibility. Subjects who meet all inclusion criteria and none of the exclusion criteria will be entered into the study.

The following treatment regimens will be used:

- Dapagliflozin: 10mg per day for 12 weeks. Subjects will return to refill drug medication and perform compliance check at 4 weeks and 8 weeks after beginning treatment.
- Control Group: Subjects will meet with a dietitian every 1-2 weeks throughout the study to discuss nutritional counseling with a goal to lose 3-5% of body weight over 12 weeks to mirror expected SGLT2

inhibitor-derived weight loss over the same period. During these hour-long sessions, volunteers will learn how to adjust their eating habits by following the recommendations of the American Heart Association for reducing dietary fat and substituting complex carbohydrates and reducing energy intake to induce gradual weight loss while maintaining recommended dietary composition. Volunteers also will receive education on portion sizes, meal timing, and meal preparation. Participants receive a notebook of course content and will weigh in prior to each session. Additional counseling visits and/or phone calls may be instituted if desirable weight loss is not achieved. Subjects may be asked to record their dietary intake for a 24-hour period throughout the intervention for review by the dietitian.

Total duration of subject treatment will be 12 weeks. Total duration of the study is expected to be 16-18 weeks.

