7.2. Statistical Methods

Analytical Approach.

Experimental results will be expressed as means ± SE. Comparisons of means between all the groups will be done by ANCOVA. Associations, within a group, between aging-related biomarkers vs metabolic outcomes and vs. healthspan outcomes will be determined by Pearson's correlation. For tests of correlation coefficients between groups, we will use the Fisher's Z transformation. We will also determine the relationship between aging-related biomarkers vs metabolic outcomes and vs. healthspan outcomes, by using multiple regression analysis. Scatter plots will be done to look for outliers and to verify linearity.

We will use natural logarithmic transformation to evaluate median percent change. This pilot study is not powered to achieve statistical significance with a p <0.05 and is of exploratory nature. The data included in this study will be only of completers. A larger trial in the future based on this pilot data would follow an intention-to-treat analysis.

The Biostatistics Core of the San Antonio Pepper Center, led by [name], will guide the statistical analyses.

8. Safety and Adverse Events

8.1. **Definitions**

Unanticipated Problems Involving Risk to Subjects or Others (UPIRSO)

Any incident, experience, or outcome that meets all of the following criteria:

- Unexpected in nature, severity, or frequency (i.e. not described in study-related documents such as the IRB-approved protocol or consent form, the investigators brochure, etc.)
- Related or possibly related to participation in the research (i.e. possibly related means there is a reasonable possibility that the incident experience, or outcome may have been caused by the procedures involved in the research)
- Suggests that the research places subjects or others at greater risk of harm (including physical, psychological, economic, or social harm).

Adverse Event (AE)

In general, AE is used very broadly and encompasses physical and psychological harms and includes:

Any untoward or unfavorable medical occurrence in a human subject, including any abnormal sign (for example, abnormal physical exam or laboratory finding), symptom, or disease, temporally associated with the subject's participation in the research, whether or not it is considered related to the subject's participation in the research.

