8.3. Reporting of Serious Adverse Events and Unanticipated Problems

Each participant will be evaluated for any adverse events (AE). Any incidents, experiences, and outcomes either reported by the subject to the PI or designated research staff or medical staff caring for the subject, and which meet AE criteria will be documented. Any AE reported as serious (SAE) requires submitting a Prompt Report Form to the IRB and, if deemed appropriate by PI, SAE and or unanticipated risks to subjects or others (UPIRSO) may be reportable to the Pepper Center DSMB. A copy of the SAE or UPIRSO prompt report is submitted to the Pepper DSMB for review as well as the NIA Program Officer within 24 hours of notification to PI. All AE that are not serious or UPIRSO will be summarized annually and submitted to the IRB and R&D Committees.

SAE and or UPIRSO will be reported per IRB policy and procedure. Events that do not involve AE or SAE (non-AE UPIRSO), and which are a result of study participation are also promptly reported to the IRB per local policy. The report will include a description of the event, when and how it was reported, as well as any official chart records or documentation to corroborate the event or the reporting of the event. All AE will be graded as mild, moderate, or severe. Any action resulting in a temporary or permanent suspension of this study (e.g. local site IRB actions) will be reported to FDA per IRB stipulations. Additionally, the PI will report SAE to the drug sponsor Astra-Zeneca.

Serious adverse events (SAE) still ongoing at the end of the study period will be followed up to determine the final outcome and or referred to participants' primary care provider. Any SAE that occurs after the study period that is considered to be possibly related to the study treatment or study participation will be recorded and reported per Institutional policy and according to FDA requirements.

Investigator responsibilities - The PI is responsible for:

- Reviewing all incidents, experiences, and outcomes that may represent UPIRSO.
- Determining whether event represents a possible UPIRSO
- Promptly reporting to IRB per local policy
- Contacting institutions involved
- Implementing actions necessary to eliminate immediate hazard
- Submitting follow up reports to IRB
- Submitting amendments to IRB, if applicable or stipulated

Version: 2.4 10-29-2020

Report SAE and UPIRSO immediately by phone and or secure email to:

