8.5.1. Designated Safety Officer

- Assess SAE or SAE-UPIRSO to determine if prompt reporting is required and, if yes, notify pharmacist to halt dispensing until further information is obtained.
- Compare event data to intervention/assignment to determine if SAE is related to study intervention
- Assess study and subject safety to determine if stopping rules should be invoked
- Create the Safety Officer record without personal identifiers and communicate to Sponsor Investigator and Clinical Study Coordinator with overall impression and recommended plan of action

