8.5.4. Clinical Study Coordinator

- Obtain a copy of Safety Officer or DSMB report/record to file in study binder/file and forward a copy to the Regulatory Coordinator
- Ensure appropriate medical care and follow up is scheduled and implemented until SAE resolved

Version: 2.4_10-29-2020

Create FDA report, if applicable

HSC 20190766H Version: 2.4 10-29-2020

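### Section 8.2 lets an unmasked causality decision end follow-up of an unresolved non-serious adverse event, so its recorded course and outcome may cover different lengths by arm

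*Combined protocol and SAP*

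**What the plan says.** - **What counts as an AE.** Section 8.1 defines an AE "whether or not it is considered related to the subject's participation in the research". Section 8.2 records all AEs in the study period and asks about them at each contact.
- **When follow-up ends.** Under section 8.2 each event is "followed until resolution, stabilization, or until it has been determined that the study treatment or participation is not the cause".
- **SAEs in section 8.2.** The next sentence adds: "SAEs that are still ongoing at the end of the study period will be followed up to determine the final outcome". It carries no causality condition.
- **SAEs in section 8.3.** The parallel sentence reads "followed up to determine the final outcome and or referred to" the participant's primary care provider.
- **SAEs in section 8.5.4.** The coordinator's task is: "Ensure appropriate medical care and follow up is scheduled and implemented until SAE resolved".
- **Masking.** Section 3.2: "This is a single center, open-label, randomized controlled trial". For SAEs, section 8.5.1 has the Designated Safety Officer "Compare event data to intervention/assignment to determine if SAE is related to study intervention". The plan does not name who judges causality for non-serious AEs.
- **Use of the data.** Section 8.3 has every AE graded mild, moderate or severe, and non-serious AEs summarized annually for the IRB and R&D committees. Section 10.1 has AE summaries sent to the DSMB on request. Section 7 plans no safety comparison between arms.

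**The concern.** The plan captures AEs regardless of cause but may stop describing them because of presumed cause. In an open-label trial that judgement can be tied to the arm. Section 3.4 lists urinary tract infection, genital mycotic infection and low blood sugar among the dapagliflozin risks. An infection of this kind in a counseling participant could be ruled unrelated and closed, while the same infection on dapagliflozin stays open. The reverse is also possible: staff who expect no drug link may close a drug-arm event early. No rule requires a closed event to be reopened if it worsens.

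At stake is the comparability of recorded duration, later worsening and outcome of non-serious events. A mistaken early call of unrelated would also end the tracking of an event that may later prove drug-related. With 20 completers split evenly, or 10 per arm, one or two incompletely described events can alter the descriptive safety picture.

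**Working it through.** The plan states no figure on this point, so the check sets the passages side by side.

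**1. Is the causality opinion sufficient alone?** Yes. Section 8.2 lists three end points joined by or. The third does not require that the event has resolved or stabilized.

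**2. Can the person deciding know the arm?** Yes, for every role described. The trial is open-label. Under section 5.2 the coordinator hands out drug, and study investigators make the compliance calls that also monitor AEs. Under section 8.2 the site investigator reviews AEs. Under section 8.5.1 the safety officer uses the assignment explicitly. For non-serious AEs arm awareness is an inference, since the assessor is unnamed, but no masked role appears anywhere.

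**3. Does the rule reach SAEs?** Only unclearly. The SAE sentence in section 8.2 covers those still ongoing at the end of the study period, whatever their cause. For an SAE judged unrelated earlier, two readings are open: the SAE sentence overrides the general rule, or the general rule has already closed the event. The text does not settle this.

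**4. Does the rule cut short the count of events?** No. All AEs in the study period are recorded and all participants receive calls every two weeks. Section 8.3 requires a prompt IRB report for any SAE without a relatedness condition. A closed event that becomes serious during the study is therefore reportable. What can be lost is its link to the earlier entry.

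**5. Do the SAE passages agree?** Section 8.2 calls for the final outcome. The and/or wording in section 8.3 can be read as letting referral stand in for it. Section 8.5.4 concerns arranging care and follow-up, and need not be read as a third data-collection end point.

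**6. Can the size be estimated?** For arm j, let N be the number of AEs, w the share that later worsen, p_j the share closed early as unrelated, and c the share of later worsenings still captured after closure.

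Recorded worsenings: R_j = N × w × [1 − p_j × (1 − c)]

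With equal N and w, the drug-to-control ratio is [1 − p_D(1 − c)] / [1 − p_C(1 − c)].

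The ratio is 1 if p_D = p_C or if c = 1. It exceeds 1 if more control events are closed early, and falls below 1 if more drug-arm events are. The documents give none of w, p_D, p_C or c, so neither size nor sign follows from them.

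**The case against.** The strongest case against is that the rule has little reach.

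- **Participation is in the rule.** Follow-up stops only if treatment and participation are both ruled out. Controls have the same biopsies and blood draws plus a weight-loss program, so their events are not automatically unrelated. This stands as a limit on any predicted direction. It does not remove the possible asymmetry for events listed as drug risks.
- **SAEs are protected.** This largely stands. A reader might infer that follow-up of harms in general, or escalation to serious events, is hidden by the rule. Sections 8.2 and 8.3 do not support that, apart from the SAE judged unrelated before study end and the referral wording.
- **Repeated questioning catches worsening.** This stands in part. A worsening may resurface as a new AE, but nothing requires it to be joined to the closed one.
- **No safety analysis depends on it.** This stands. No endpoint in section 3.3 is a safety endpoint. Section 8.3 requires a grade without saying that it must be the worst grade.

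A reader might also infer a several-fold distortion between arms. Suppose 80% of control AEs and 30% of drug AEs are closed early. With c = 0 the ratio is 0.70 / 0.20 = 3.5. With c = 0.8 it is 0.94 / 0.84 = 1.12, and with c = 1 it is 1. Every input is assumed and the answer turns on c, so no such ratio should be cited as an estimate.

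**Conclusion.** The point holds for non-serious AEs. An unmasked causality decision can end follow-up of an event that has neither resolved nor stabilized, so its course, later worsening and outcome may be recorded over different lengths by arm. For SAEs judged unrelated before study end, the text is unclear.

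Occurrence of AEs, and reporting of new SAEs within the study period, are unaffected. The consequence is limited to descriptive safety data in an exploratory pilot of 20 completers. It does not touch the primary outcome or any planned test. The imbalance is zero if the share and timing of unrelated decisions match between arms, and otherwise its size and direction are unknown. The conclusion assumes that whoever judges non-serious AEs can know the arm, as every described role can. It is worth correcting because the correction is cheap.

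**What to change.** 1. In section 8.2, delete the third alternative, so that every AE in both arms is followed to resolution or stabilization whatever its presumed cause.
2. Record causality as a separate field that does not end data collection.
3. If an administrative cut-off for unresolved events is wanted, count it from randomization, identically in both arms, and do not let it shorten follow-up of possibly related events. The section 8.1 reporting period is unsuitable for this. It runs to 30 days after the last administration of study treatment, which gives the counseling arm no clear anchor date. It would also newly cap possibly related events, for which section 8.2 sets no time limit. And it outlasts the scheduled visits: 12 × 7 + 30 = 114 days, about week 16, against Visit 12 at week 13.
4. Reconcile sections 8.2 and 8.3 on whether referral to primary care can replace recording the final outcome of an ongoing SAE, and state whether the rule covers an SAE judged unrelated before study end.

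The cost is a few sentences of protocol text, a few more AE status checks, and possibly a closing phone call after Visit 12. Section 6.1.5 already allows AE follow-up calls at any time. No new visit or procedure is needed.

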8.3. Reporting of Serious Adverse Events and Unanticipated Problems

Each participant will be evaluated for any adverse events (AE). Any incidents, experiences, and outcomes either reported by the subject to the PI or designated research staff or medical staff caring for the subject, and which meet AE criteria will be documented. Any AE reported as serious (SAE) requires submitting a Prompt Report Form to the IRB and, if deemed appropriate by PI, SAE and or unanticipated risks to subjects or others (UPIRSO) may be reportable to the Pepper Center DSMB. A copy of the SAE or UPIRSO prompt report is submitted to the Pepper DSMB for review as well as the NIA Program Officer within 24 hours of notification to PI. All AE that are not serious or UPIRSO will be summarized annually and submitted to the IRB and R&D Committees.

SAE and or UPIRSO will be reported per IRB policy and procedure. Events that do not involve AE or SAE (non-AE UPIRSO), and which are a result of study participation are also promptly reported to the IRB per local policy. The report will include a description of the event, when and how it was reported, as well as any official chart records or documentation to corroborate the event or the reporting of the event. All AE will be graded as mild, moderate, or severe. Any action resulting in a temporary or permanent suspension of this study (e.g. local site IRB actions) will be reported to FDA per IRB stipulations. Additionally, the PI will report SAE to the drug sponsor Astra-Zeneca.

Serious adverse events (SAE) still ongoing at the end of the study period will be followed up to determine the final outcome and or referred to participants' primary care provider. Any SAE that occurs after the study period that is considered to be possibly related to the study treatment or study participation will be recorded and reported per Institutional policy and according to FDA requirements.

Investigator responsibilities - The PI is responsible for:

- Reviewing all incidents, experiences, and outcomes that may represent UPIRSO.
- Determining whether event represents a possible UPIRSO
- Promptly reporting to IRB per local policy
- Contacting institutions involved
- Implementing actions necessary to eliminate immediate hazard
- Submitting follow up reports to IRB
- Submitting amendments to IRB, if applicable or stipulated

Version: 2.4 10-29-2020

Report SAE and UPIRSO immediately by phone and or secure email to:

8.4. Medical Monitoring

The Sponsor (or investigator initiating the study) will review the safety and progress of this study on a monthly basis or when needed if protocol deviations/violations, SAE or SAE-UPIRSO occurs. The Designated Safety Officer is [name], PhD a Professor in the Department of *Medicine*, UTHSCSA, and Staff Physician at the Audie L Murphy VA Hospital.

The PI and or Co-PI will review source documentation in the research record and or medical record when study coordinator provides an electronic alert or secure email to review.

8.4.1. Investigator reporting of Protocol Deviations/Violations

Departures during the conduct of a research study constitute a protocol deviation, violation or exception and as such must be reported to the UTHSCSA IRB.

Tracking and reporting of protocol deviations and violations to the IRB is the responsibility of the PI. To determine whether deviations or violations require prompt reporting or other action, refer to the IRB document entitled "Decision Tree – Evaluating Departures" on the IRB website. Failure to report

Version: 2.4 10-29-2020

departures from the protocol according to IRB policy may constitute possible non-compliance, which will require a Prompt Report Form and possible FDA reporting by IRB.

Deviations and violations may be identified in a number of ways including:

- A report by an individual can be made directly to the IRB Office.
- The IRB may learn of event through its continuing review of ongoing research.
- Compliance reviews (audits) conducted by the Office of Regulatory Affairs and Compliance or one
 of the HSC affiliated institutional compliance offices.
- A report by an individual can be made directly to the Office of Regulatory Affairs and Compliance (Hotline) or one of the HSC affiliated institutional compliance offices.
- A report by another committee, department, institution, or official.
- An audit or report from the study sponsor or sponsor's monitoring entity.

8.4.2. Definitions of Protocol Deviations/Violations

- Protocol deviations
- Protocol violations
- Emergency violations
- For more information, refer to UTHSCSA IRB Policy website: https://research.uthscsa.edu/irb/policy/deviations

8.5. Safety Procedures

See Section 5.8 – If, in the case of SAE or SAE-UPIRSO, the Clinical Study Coordinator or appropriately designated study staff will contact the Designated Safety Officer (Section 8.6) to assess the need for stopping research activities until further information can be gathered.

8.5.1. Designated Safety Officer

- Assess SAE or SAE-UPIRSO to determine if prompt reporting is required and, if yes, notify pharmacist to halt dispensing until further information is obtained.
- Compare event data to intervention/assignment to determine if SAE is related to study intervention
- Assess study and subject safety to determine if stopping rules should be invoked
- Create the Safety Officer record without personal identifiers and communicate to Sponsor Investigator and Clinical Study Coordinator with overall impression and recommended plan of action

8.5.2. Research Drug Manager

Suspend dispensing of study drug until SAE reporting is complete

8.5.3. Sponsor Investigator

- Receive and review Safety Officer report with Clinical Study Coordinator, Pharmacist and Study Statistician
- Assess and implement stopping rules, if required
- Ensure that IRB, FDA, and funding sponsor are notified as appropriate to local or agency policy
- If applicable, notify Pepper Center DSMB

8.5.4. Clinical Study Coordinator

- Obtain a copy of Safety Officer or DSMB report/record to file in study binder/file and forward a copy to the Regulatory Coordinator
- Ensure appropriate medical care and follow up is scheduled and implemented until SAE resolved

Version: 2.4_10-29-2020

Create FDA report, if applicable

HSC 20190766H Version: 2.4 10-29-2020

